### Research Question and Aims

The objective of this study is to evaluate the efficacy of low intensity shockwave therapy (LiSWT) via MoreNova in the treatment of erectile dysfunction (ED).

Aim 1: To assess the efficacy of the use of MoreNova shockwave therapy in individuals diagnosed with ED by a change in evidence based imaging via Color Duplex Doppler Ultrasound (CDDU)

Aim 2: To evaluate the efficacy of the use of MoreNova shockwave therapy based on patient reports erectile charges through the IIEF-EF, EHS, SEP 2+3, and GAQ questionnaires (1, 3).

Background (*Include relevant experience, gaps in current knowledge, preliminary data, etc.*):

ED is broadly defined as the inability to achieve or maintain an erection sufficient for penetration (NIH Consensus Statement 1992). Treatment for ED consists of oral medications, intracavernosal injections and surgically placed penile prosthetics. In the literature this has been described as a Stepwise Approach, empirically offering therapy beginning with the least invasive treatment option. Our approach at Mayo Clinic Florida has been to investigate the complaint of ED in men who fail the first step in ED management which is a trial of oral phosphodiesterase type-5 inhibitors (PDE5I). Using evidence-based technology we rule out psychologic ED and characterize vascular erectile function. Color Duplex Doppler Ultrasound (CDDU) in combination with an age specific dosage of intracavernous vasoactive medication (alprostadil, PGE1) stimulates erection for office testing. We have been able to categorize the severity of ED and identify the etiology of ED as arteriogenic ED, veno-occlusive ED or psychogenic ED. CDDU has become the standard of care in the evaluation of vascular erectile dysfunction (2). Penile injection therapy is often taught to men who have failed oral PDE-Type 5 Inhibitors (sildenafil, vardenafil, tadalafil). These therapies do not cure ED; they manage ED with escalating dosages of vasoactive drugs. The goal of LISWT is to restore natural erections and / or improve responses to oral medications (first line therapy).

LISWT for ED is under evaluation in the USA. The European Association of Urology Guidelines on ED were recently updated to include LISWT for men with mild to moderate ED. The energy/pulse used in this application is approximately 10% of the energy used for disintegrating kidney stones; no serious side effects have been reported. Shock wave therapy for diabetic ulcers has recently been approved by the FDA.

**The present study proposal uses a device called MoreNova, in which shockwaves are focused onto linear**

**segments for improved organ coverage. Shockwaves produced by MoreNova are aimed at the penile shaft targeting the left and right corpora cavernosa and the crura. Our study is designed to identify immediate effects and short term durability of**

## LISWT as a non-pharmacologic, non-surgical means of treating erectile dysfunction secondary to mild ED.

### Study Design and Methods

**Methods:** *Describe, in detail, the research activities that will be conducted under this protocol:*

#### APPROACH

This is prospective, pilot clinical study of 10 men aimed to evaluate the efficacy of MoreNova Shockwave therapy for men diagnosed with ED. We will restrict our target population to include men only between and including the ages of 40 and 55 who have been diagnosed with ED for over a year, but less than 5 years.

*Efficacy* is to be assessed by CDDU imaging during and from treatment up to follow-ups.

*Efficacy* is to be assessed by patient reported questionnaires data via IIEF-EF, SEP 2+3, GAQ and EHS that catalog the frequency of successful erections and side effects during treatment.

#### RECRUITMENT

Review of clinic patient records within the MCF Department of Urology to identify potential research participants (patients with ED who have already presented to MCF and had initial evaluation and CDDU diagnosis). Participants will first be identified through the treating physician and the PI on this proposal, [name]. The study coordinator will then be notified of the potentially eligible patient who will further screen for eligibility. Once the patient has been determined eligible, the study coordinator will contact the potential study participant to schedule a research appointment to discuss the study in detail. The study coordinator will meet with the patient, describe the goals of the study, and ask if they would like to participate. If the patient agrees to participate at this time, a signed Patient Informed Consent is obtained before the patient leaves. The patient can decide at a later date to sign Informed Consent. If so, the study coordinator will schedule an appointment at a time when the patient will return for an appointment with a consultant. Recruitment will take place in quiet room where the study will be explained fully and the patient will have adequate time to decide. If a patient declines consent, the study coordinator will express that this in no way affects their current or future medical care.

Given the paperless initiative put forth by the clinical studies units, this study will utilize the Research Participant Tracking (PTrax) digital signature capture feature.

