#### PARTICIPATION

Once consented, the participants' medical history will be reported and a physical examination will be performed as part of standard of care. Participants will be asked to stop all PDE-5 inhibitors or injectable vascular stimulants for 1 week prior to first treatment (washout period) and throughout the treatments. The participant will then be scheduled to receive their first shock wave therapy via the MoreNova device. Participants will receive a total of 6 treatments lasting approximately 20 minutes each, two treatments weekly for 3 weeks. A CDDU diagnostic will

be reviewed in clinical records (within 12 months prior to study enrollment). CDDU will be repeated as part of the study at the final treatment and at the 3-4-month follow-up. Below is test schedule for study participants.

	Baseline	Treatment 1-5	Treatment 6	Follow-Up 1 month	Follow-up 3-4 month
Level 4 Evaluation/Consult H&E	X a				
Return Physical (Level 2 Return)		X	X		
Washout period		X b	X	X	
MoreNova Therapy		X	X		
Color Duplex Doppler Ultrasound (CDDU) Exam	X a		X		X
Questionnaires c	X a		X a	X a	X a
Adverse Events		X	X	X	X
Concomitant Medications	X	X	X	X	X

astandard of care

bBegin one-week **prior** to treatment 1

cIIEF-EF, EHS, SEP 2+3, and GAQ

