### FUNDING

For this proposal we are requesting funding through the Florida Comprehensive Focus Research Team for a total of **\$36,969.60**. Below is a breakdown of the approximated expected costs.

- Color Duplex Doppler Ultrasound (CDDU): ~\$728.48 per exam x 2 research exams per participant= \$1,456.92 per participant x 10 total enrolled= **\$14,569.60**
- Return Level 3 Office Visit: ~\$250 per visit x 6 visits= \$750.00 per participant x 10 total enrollment= **\$7,500**
- Clinical Research Coordinator (CCRC) .10 FTE for 1.5 years= ~**\$10,016**
- Clinical Research Assistant .10 FTE for 1.5 years= ~**\$4,884**

*To note, these are estimated costs and may not be reflective of true coordinator and data entry support.*

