#### Inclusion Criteria:

1. The patient must have given his informed and signed written consent
2. The patient is a male
3. Between 40 to and including 55 years of age
4. The patient has ED for longer than 1 year but less than 5 years.
5. The patient is PDE5i responsive, meaning he is able to achieve and maintain an erection under the effect of the maximal dosage of PDE5i
6. IIEF-EF Domain score of 17-20
7. Evidence Based Criteria: Doppler Clinical Exam

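### The clinic CDDU that qualifies a man is also the only baseline for the primary change, so admission on its abnormal side would be expected to look like improvement with no treatment effect

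*Protocol*

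**What the plan says.** Aim 1 judges efficacy "by a change in evidence based imaging via Color Duplex Doppler Ultrasound (CDDU". The APPROACH section describes the design: "This is prospective, pilot clinical study of 10 men". No control or sham group appears.

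Under RECRUITMENT, candidates are found by chart review among "patients with ED who have already presented to MCF and had initial evaluation and CDDU diagnosis". Inclusion item 7 reads "Evidence Based Criteria: Doppler Clinical Exam". Exclusion item 10 uses exactly the same words. Neither gives a value.

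Under PARTICIPATION, the pre-treatment CDDU is to "be reviewed in clinical records (within 12 months prior to study enrollment"), and the test schedule marks the baseline CDDU as standard of care. The section continues: "CDDU will be repeated as part of the study at the final treatment and at the 3-4-month follow-up". FUNDING agrees, since it pays for "2 research exams per participant". The Primary Endpoint section names the same three exams (clinic, last treatment, 3-4 months) and treats them together as the evidence that erectile function has improved.

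**The concern.** A single Doppler exam is a man's usual level plus the variation of that day. If men are chosen because the exam looked abnormal, the chosen readings are on average somewhat worse than those men's usual level, and a second exam tends to move back with no treatment at all. When the qualifying exam is also the baseline, that movement is counted as change.

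This is a separate matter from the age of the clinic exam: it would arise with an exam one day old. The investigator both helps to identify candidates and performs the ultrasound, so the baseline reading can be in view when a man is chosen. All men are treated, so nothing in the design separates this movement from a treatment effect.

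**Working it through.** **Plan's own figure.** There is none to reproduce. The Data Analysis section gives no power calculation, and the Protocol states no Doppler cut-off, SD, repeatability or significance level.

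**From the Protocol.** n = 10, one group, one pre-treatment CDDU (the clinic exam), two study CDDUs.

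**Assumed.** The clinic reading X1 and a later reading X2 are bivariate normal with equal mean and SD and correlation ρ between exams. Each is coded so that higher is better, and there is no treatment effect. Men are admitted if X1 lies between a and b (in SD units).

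**Formula.** Expected change = −(1 − ρ) × m, where m = [φ(a) − φ(b)] / [Φ(b) − Φ(a)]. For admission of the lowest fraction q this becomes (1 − ρ) × φ(z_q) / q.

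**Numbers put in.**
- Lower half: φ(0)/0.5 = 0.399/0.5 = 0.798. At ρ = 0.5 the shift is 0.5 × 0.798 = +0.40 SD; at ρ = 0.9 it is 0.1 × 0.798 = +0.08 SD.
- 20th to 50th percentile: m = (0.280 − 0.399)/0.3 = −0.397. At ρ = 0.5 the shift is +0.20 SD; at ρ = 0.9 it is +0.04 SD.
- Lowest quarter: 0.318/0.25 = 1.271. At ρ = 0.5 the shift is +0.64 SD.
- Only the worst 20% excluded: m = 0.280/0.8 = +0.350. At ρ = 0.5 the shift is −0.175 SD.

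**Results.** Each cell gives the expected change in SD. In brackets is the share of simulated null trials (n = 10) in which a two-sided 5% paired t-test shows significant improvement; the nominal share in that direction is 2.5%. The simulation used 40,000 trials per cell, and 20,000 for the lowest quarter.

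| Clinic readings admitted | ρ = 0.5 | ρ = 0.7 | ρ = 0.8 | ρ = 0.9 |
|---|---|---|---|---|
| Lowest quarter | +0.636 (51%) | not run | +0.254 (22%) | not run |
| Lowest 30% | +0.579 (44%) | +0.348 (27%) | +0.232 (19%) | +0.116 (11%) |
| Lower half | +0.399 (23%) | +0.239 (15%) | +0.160 (11%) | +0.080 (7%) |
| Lowest 70% | +0.248 (11%) | +0.149 (8%) | +0.099 (7%) | +0.050 (5%) |
| 20th to 50th percentile | +0.198 (9%) | +0.119 (7%) | +0.079 (6%) | +0.040 (4%) |
| 20th to 80th percentile | 0 (2.5%) | 0 (2.4%) | 0 (2.5%) | 0 (2.4%) |
| All but the worst 20% | −0.175 (0.7%) | −0.105 (0.9%) | −0.070 (1.2%) | −0.035 (1.5%) |

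**Check on the cause.** Men were selected on the clinic reading (lower half, ρ of 0.5, 0.7 and 0.8), but the change was counted from a separate pre-treatment exam. The expected change was then 0.00 SD, with significant improvement in about 2.5% of trials. The shift comes from using one exam twice.

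**The case against.** The strongest case against concerns direction. A reader might infer that the bias always favours benefit. The documents do not support that. No Doppler threshold is stated, and the same words serve as an inclusion and an exclusion criterion. The Background counts psychogenic ED among the CDDU categories, although it also says that psychologic causes are ruled out. Selection towards abnormal readings is the natural reading of a recruitment rule built on a CDDU diagnosis, but it remains an inference. As the table shows, other windows give zero or a negative shift. This objection stands and limits the point to a conditional one.

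The second objection concerns size. A reader might take the 51% figure as this trial's false-positive rate. It is not. The study targets mild ED (IIEF-EF 17-20, PDE5i-responsive), so admitting only the lowest quarter of clinic Doppler readings is an unlikely extreme. The model also selects on the very measure that is analysed. The Primary Endpoint section names several Doppler measures and a hardness score, and selection on one carries over only partly to the others. The Protocol specifies no paired t-test. This also stands: the percentages illustrate a range and estimate nothing.

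Two further objections do not remove the point. Pilot status excuses the absence of a power calculation, but the stated aim is efficacy and the primary endpoint is read as evidence of it. A later SAP could add a sensitivity analysis, but the Protocol fixes which exam is the baseline, and no analysis can supply a pre-treatment exam that was never done.

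**Conclusion.** The point holds in conditional form. The qualifying CDDU and the baseline CDDU are the same exam, in 10 treated men with no comparator. If admission is on the abnormal side, the expected primary change with no treatment effect is favourable.

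Under the assumed correlations of 0.5 to 0.9, the plausible milder windows give +0.04 to +0.20 SD (20th to 50th percentile; 4-9% false significant improvement) and +0.08 to +0.40 SD (lower half; 7-23%). The upper extreme shown is +0.64 SD (51%). Which of these applies, and even the sign, depends on a Doppler window that the Protocol does not give. What follows firmly is that the change from the clinic CDDU cannot by itself carry a claim of efficacy.

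**What to change.** 1. In the Primary Endpoint section, state that the change from the clinic CDDU is descriptive and will not by itself be called efficacy or evidence of improvement.
2. Report that change beside a sensitivity range for the shift expected from selection, over stated assumptions for the between-exam correlation and for the Doppler window actually applied at admission.
3. Reconcile inclusion item 7 with exclusion item 10, so that this window is known to the reader.
4. The contrast from Treatment 6 to 3-4 months may be shown as free of this selection, but only as durability. Note beside it that the test schedule marks washout at Treatment 6 and not at 3-4 months.

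The between-exam variation should not be estimated from the two study exams to correct the result. Both follow treatment, so durability and the washout difference are mixed in. Ten pairs leave 9 degrees of freedom, and the 95% interval for an SD then runs from about 0.69 to 1.83 times its estimate. Nor does taking another reading from the same clinic exam as the baseline solve the problem, because men are recruited on that exam as a whole.

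The cost is a few sentences and a short calculation, with no added exam or patient; the primary result will be reported less favourably. A separate pre-treatment study CDDU would remove this artefact, though not other uncontrolled effects over time. At the FUNDING price it would cost $728.48 × 10 = $7,284.80, plus one more injected exam per man. The fix above does not depend on it.

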#### PARTICIPATION

Once consented, the participants' medical history will be reported and a physical examination will be performed as part of standard of care. Participants will be asked to stop all PDE-5 inhibitors or injectable vascular stimulants for 1 week prior to first treatment (washout period) and throughout the treatments. The participant will then be scheduled to receive their first shock wave therapy via the MoreNova device. Participants will receive a total of 6 treatments lasting approximately 20 minutes each, two treatments weekly for 3 weeks. A CDDU diagnostic will

be reviewed in clinical records (within 12 months prior to study enrollment). CDDU will be repeated as part of the study at the final treatment and at the 3-4-month follow-up. Below is test schedule for study participants.

	Baseline	Treatment 1-5	Treatment 6	Follow-Up 1 month	Follow-up 3-4 month
Level 4 Evaluation/Consult H&E	X a				
Return Physical (Level 2 Return)		X	X		
Washout period		X b	X	X	
MoreNova Therapy		X	X		
Color Duplex Doppler Ultrasound (CDDU) Exam	X a		X		X
Questionnaires c	X a		X a	X a	X a
Adverse Events		X	X	X	X
Concomitant Medications	X	X	X	X	X

astandard of care

bBegin one-week **prior** to treatment 1

cIIEF-EF, EHS, SEP 2+3, and GAQ

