## DATA COLLECTION

Clinical data will be collected begin at time of consent from the patients' medical record as well as the administered questionnaires. All data obtained for this investigation will be entered and maintained into electronic case report forms via REDCap database. Clinical data collection will include subject demographics (age, gender, race/ethnicity), current medications, and medical history relevant to cancer risk such as smoking history, body mass index, and family history of cancer. In addition, we will collect clinically variables resulting from the CDDU exam (see primary endpoint). The participant questionnaire responses will also be entered. Follow-up data collection for outcomes on all participants will be performed at 3-4 months after the last treatment was given.

All data will be entered by approved study staff. Continuous data queries will be performed to ensure data integrity and completion.

**Resources:** *Describe the available resources to conduct the research (personnel, time, facilities, mentor commitment, etc.):* This proposal will require collaborative efforts between the Department of Urology and Clinical Studies Unit. For this proposal we will utilize the existing research infrastructure nestled within the Department of Urology. A clinical research coordinator will assist in screening, consenting, and enrollment and follow-up data and AE collection for all participating patients. Our Urology Senior Program Coordinator will

provide oversight and management to ensure timely and on budget study completion. Staff from the Urology Department will administer MoreNova shockwave therapy.

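### PDE5 inhibitors and injectables are unrestricted before the 3–4-month questionnaires, and the text and printed schedule end the drug stop at different times

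*Protocol*

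**What the plan says.** Under PARTICIPATION in the Protocol, consented men must "stop all PDE-5 inhibitors or injectable vascular stimulants for 1 week prior to first treatment (washout period) and throughout the treatments". No later restriction appears in the text.

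The test schedule in the same section has a row for the "washout period". As printed it carries three marks: Treatment 1-5, Treatment 6 and the 1-month follow-up. Baseline and the 3–4-month follow-up are blank. The footnote on the first mark reads "Begin one-week prior to treatment 1". The row "Concomitant Medications" is marked in all five columns, and DATA COLLECTION lists "current medications" among the items gathered.

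Questionnaires (IIEF-EF, EHS, SEP 2+3, GAQ) are given at baseline, at Treatment 6, at 1 month and at 3–4 months. DATA COLLECTION adds: "Follow-up data collection for outcomes on all participants will be performed at 3-4 months after the last treatment was given".

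Two entry rules bear on the point. Inclusion criterion 5 is "The patient is PDE5i responsive, meaning he is able to achieve and maintain an erection under the effect of the maximal dosage of PDE5i". Criterion 6 is "IIEF-EF Domain score of 17-20", without saying whether that score is on or off drug.

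The background names two goals: the return of unaided erections, and a better response to oral drugs. It presents the study as one of immediate effect and short-term durability of a treatment that is not a drug.

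**The concern.** A man who follows the protocol exactly may go back to a drug known to work for him before he completes the last questionnaires. A maintained or higher score at 3–4 months could then come from lasting shockwave effect, from the drug, or from both. With one group of 10 men, no comparison arm would show a shift due to resumed drug use.

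The two goals need different drug states: unaided erections are judged off drug, better oral-drug response on drug. The protocol does not say which of these the 3–4-month scores represent.

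This is a conduct rule as much as an analysis matter. A statistical analysis plan, which is not shown here, could sort assessments by drug use, but it cannot create drug-free assessments that nobody was asked to provide.

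**Working it through.** The protocol gives no figure of its own to reproduce on this point, so the first step is to set the sources side by side.

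**1. Is the drug stop in force when questionnaires are given?**

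| Questionnaire time | Text | Schedule as printed | Schedule, marks moved one column left |
|---|---|---|---|
| Baseline | not covered | blank | marked |
| Treatment 6 | covered | marked | marked |
| 1 month | not covered | marked | blank |
| 3–4 months | not covered | blank | blank |

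The last column tests a table-reading error. A move to the left would remove the 1-month mismatch and weaken the baseline point. A move to the right would put the footnote about starting before Treatment 1 on Treatment 6, which makes no sense. The 3–4-month gap is in every tenable column.

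**2. Baseline.** Under RECRUITMENT, eligibility is settled before the man is approached for consent; the drug stop is introduced for consented men. The entry IIEF-EF therefore seems to precede the washout. The protocol does not, however, fix the order of the baseline questionnaires relative to the washout week.

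**3. Length of the stop.** Session spacing is an assumption. Two sessions a week on fixed weekdays for 3 weeks span 14 days plus the gap within a week.
- Gap of 1 to 6 days: span 15 to 20 days; a gap of 3 days gives 17.
- Drug-free time by Treatment 6: 7 + 17 = 24 days (range 7 + 15 = 22 to 7 + 20 = 27).
- To the 1-month visit, if the printed schedule applies and a month is 28 to 31 days: 24 + 28 = 52 to 24 + 31 = 55 days (full range 22 + 28 = 50 to 27 + 31 = 58).
- Unrestricted time before the last questionnaires: 3–4 months under the text, 2–3 months under the printed schedule.

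**4. Sensitivity for IIEF-EF.** Let d be the points a drug adds in a user, and m the number of men on drug at 3–4 months minus the number on drug at baseline. Both are assumptions; the protocol gives neither. With n = 10 and the same d at both times, the shift in mean change is d × m / 10.

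| | d = 2 | d = 4 | d = 6 |
|---|---|---|---|
| m = 0 | 0 | 0 | 0 |
| m = 1 | 0.2 | 0.4 | 0.6 |
| m = 3 | 0.6 | 1.2 | 1.8 |

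A negative m reverses the sign.

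**5. What a one-week interval leaves.** If drug influence is proportional to the part of the recall window lying before the interval, the share left for a recall of R weeks is 1 − 1/R. That is 0% at R = 1, 50% at R = 2 and 75% at R = 4 (R is assumed). For d = 4 and m = 3, the 1.2 points become 0, 0.6 or 0.9.

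**The case against.** **The 1-month mismatch may be an artefact.** Moved one column left, the washout row agrees with the text. This stands as a possibility. Against it, the other rows read sensibly and the footnote fits its printed place. A reader might infer a proven contradiction; one cell of a table read from PDF does not prove it. The 3–4-month gap does not depend on that cell.

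**The entry score may already be off drug.** Men who manage an erection on maximal dose yet score 17–20 were plausibly scored without the drug. That is a fair inference, but the protocol does not say so. A reader might equally infer that baseline was on drug; that is not stated either. What stands is that the baseline drug state is not fixed.

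**On-drug follow-up serves a stated goal.** Better response to oral drugs is one of the two goals, so drug use at 3–4 months is not wrong in itself. This stands. On-drug assessments should be kept and reported for that goal, not discarded.

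**Medication use is recorded, and separating it is analysis-plan work.** The recording is a real strength. It lets an analyst label scores, but it does not supply drug-free ones.

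**The consequence is limited.** This also stands. The primary Doppler measures follow a fixed 10 mcg alprostadil injection, the study is a 10-man pilot, and placebo response and regression to the mean would remain whatever is done about drugs.

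**Conclusion.** The point holds as a gap in the drug-stop rule that affects the secondary endpoint and should be fixed. The firm part is that no reading of the text or schedule restricts PDE5 inhibitors or injectables before the 3–4-month questionnaires, in men selected for responding to PDE5 inhibitors and with no control group. The 1-month mismatch holds as printed, and the baseline drug state is unspecified.

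A reader might go further and conclude that the 3–4-month scores will be biased upward. The document does not support that. If drug use is equal at baseline and at 3–4 months, the net shift in the sensitivity calculation is zero; if more men use the drug at baseline, the shift is downward. The figures of 0.2 to 0.6 points per net user rest on assumed drug effects and on the same effect at both times. They show scale only and do not estimate bias. No estimate is made for the Doppler measures, where the fixed injection largely standardises the drug state.

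**What to change.** 1. Give one end date for the drug stop, the same in the text and the schedule, and say whether it covers the 1-month follow-up.
2. Require the existing one-week interval free of PDE5 inhibitors and injectables before the 3–4-month questionnaires, and before the 1-month questionnaires if the stop does not already cover them. Exempt the diagnostic alprostadil given for the Doppler examination. Mark the interval in the schedule.
3. Repeat the questionnaires at Treatment 1, before the first shockwave and at the end of the existing washout, and use these as the drug-free comparison. Keep the screening IIEF-EF for eligibility.
4. Use the concomitant-medication record to report any on-drug assessment separately, as evidence on the oral-drug-response goal and not as durability of unaided erections.

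The cost is protocol wording and one more questionnaire completion at a visit already planned. Against the text, the extra drug-free time is 7 + 7 = 14 days per man, or 24 + 14 = 38 days in all with the 17-day treatment span. If the printed schedule's month is kept, it is 7 extra days, or 52 + 7 = 59 to 55 + 7 = 62 days in all. Some men may not comply, leaving fewer than 10 drug-free changes, and some drug influence remains if the questionnaires' recall period exceeds one week.
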